#### 14.6 QUALITY ASSURANCE AND QUALITY CONTROL

---

In addition to the Clinical Monitoring component of this protocol, the Sponsor's Quality Assurance (QA) department shall establish an Auditing Plan document separate from the protocol to establish the criteria by which

independent auditing shall be conducted during the conduct of the trial to assess compliance with GCP and applicable regulatory requirements. Data or documentation audited shall be assessed for compliance to the protocol, accuracy in relation to source documents and compliance to applicable regulations.

Each trial site shall be required to have Standard Operating Procedures (SOP's) to define and ensure quality assurance/control processes for trial conduct, data generation & collection, recording of data/documentation and reporting according to the protocol, GCP and any applicable local, national or international regulations.

#### 14.7 DISCLOSURE AND PUBLICATION POLICY

---

All information provided regarding the trial, as well as all information collected/documentated during the course of the trial, will be regarded as confidential. The Sponsor reserves the right to release literature publications based on the results of the trial.

A clinical trial report will be prepared upon completion of the study. The Sponsor will disclose the trial results, in the form of a clinical trial report synopsis, to the IEC and the applicable regulatory authorities within one year of the end of the trial. The format of this synopsis and that of the clinical trial report and its addendum will comply with ICH E3 guidelines for structure and content of a clinical trial report.

The financial disclosure information will be provided to the Sponsor prior to trial participation from all PIs and Sub-Investigators who are involved in the trial and named on the FDA 1572 form.

By conducting this study, the Investigator affirms to the Sponsor that he or she will maintain, in strict confidence, information furnished by the Sponsor including data generated from this study and preliminary laboratory results, except as exempted for regulatory purposes.

All data generated during the conduct of this study is owned by the Sponsor and may not be used by the Investigator or affiliates without the expressed written consent of the Sponsor.

All manuscripts, abstracts, or other presentation materials generated by site investigators must be reviewed and approved by the Sponsor prior to submission.

## Contraceptive Guidelines and Pregnancy

### **Women Not of Childbearing Potential are Defined as Follows:**

Women are considered post-menopausal and not of child bearing potential if they have had 12 months of natural (spontaneous) amenorrhea with an appropriate clinical profile (e.g. age appropriate, history of vasomotor symptoms) or six months of spontaneous amenorrhea with serum FSH levels > 40 mIU/mL [for US only: and estradiol < 20 pg/mL] or have had surgical bilateral oophorectomy (with or without hysterectomy) at least six weeks ago. In the case of oophorectomy alone, only when the reproductive status of the woman has been confirmed by follow up hormone level assessment is she considered not of child bearing potential.

### **Contraceptive Guidelines for Women of Child-Bearing Potential:**

Women of child-bearing potential, defined as all women physiologically capable of becoming pregnant, must use highly effective contraception during the study and for 30 days after stopping treatment. The highly effective contraception is defined as either:

1. True abstinence: When this is in line with the preferred and usual lifestyle of the patient. Periodic abstinence (e.g., calendar, ovulation, symptothermal, post-ovulation methods) and withdrawal are not acceptable methods of contraception.
2. Sterilization: have had surgical bilateral oophorectomy (with or without hysterectomy) or tubal ligation at least six weeks ago. In case of oophorectomy alone, only when the reproductive status of the woman has been confirmed by follow up hormone level assessment.
3. Male partner sterilization (with the appropriate post-vasectomy documentation of the absence of sperm in the ejaculate). For female subjects on the study, the vasectomised male partner should be the sole partner for that patient.
4. Oral contraception, injected or implanted hormonal methods.
5. Use of a combination of any two of the following (a+b):
  - a. Placement of an intrauterine device (IUD) or intrauterine system (IUS).
  - b. Barrier methods of contraception: Condom or Occlusive cap (diaphragm or cervical/vault caps) with spermicidal foam/gel/film/cream/vaginal suppository.

The following are **unacceptable** forms of contraception for women of childbearing potential:

- Female condom
- Natural family planning (rhythm method) or breastfeeding
- Fertility awareness
- Withdrawal
- Cervical shield

Women of child-bearing potential must have a negative serum pregnancy test at baseline and a negative urine pregnancy test prior to each dosing.

**Fertile Males:**

Fertile males, defined as all males physiologically capable of conceiving offspring must use condom during treatment, and for an additional 4 weeks after study drug discontinuation, and should not father a child in this period.

**Pregnancies**

To ensure patient safety, each pregnancy in a patient on study treatment must be reported to TG Therapeutics Inc. within 24 hours of learning of its occurrence. The pregnancy should be followed up for 3 months after the termination of the pregnancy to determine outcome, including spontaneous or voluntary termination, details of the birth, and the presence or absence of any birth defects, congenital abnormalities, or maternal and/or newborn complications.

Pregnancy should be recorded on a Clinical Study Pregnancy Form and reported by the investigator to TG Therapeutics Inc. Pregnancy follow-up should be recorded on the same form and should include an assessment of the possible relationship to the study drug and reported by the investigator to TG Therapeutics Inc. Any SAE experienced during pregnancy must be reported on the SAE Report Form.

Pregnancy outcomes must be collected for the female partners of any males who took study treatment in this study. Consent to report information regarding these pregnancy outcomes should be obtained from the mother.

## 17 APPENDIX B

---

### New York Heart Association (NYHA) Classifications

Class	Functional Capacity	Objective Assessment
I	Subjects with cardiac disease but without resulting limitations of physical activity. Ordinary physical activity does not cause undue fatigue, palpitation, dyspnea, or anginal pain.	No objective evidence of cardiovascular disease.
II	Subjects with cardiac disease resulting in slight limitation of physical activity. They are comfortable at rest. Ordinary physical activity results in fatigue, palpitation, dyspnea, or anginal pain.	Objective evidence of minimal cardiovascular disease.
III	Subjects with cardiac disease resulting in marked limitation of physical activity. They are comfortable at rest. Less than ordinary activity causes fatigue, palpitation, dyspnea, or anginal pain.	Objective evidence of moderately severe cardiovascular disease.
IV	Subjects with cardiac disease resulting in inability to carry on any physical activity without discomfort. Symptoms of heart failure or the anginal syndrome may be present even at rest. If any physical activity is undertaken, discomfort is increased.	Objective evidence of severe cardiovascular disease.

Source: The Criteria Committee of New York Heart Association. Nomenclature and Criteria for Diagnosis of Diseases of the Heart and Great Vessels. 9th Ed. Boston, MA: Little, Brown & Co; 1994:253-256.

## 18 APPENDIX C

### 2010 Revised McDonald Diagnostic Criteria for MS[12]

Clinical (Attacks)	Lesions	Additional Criteria to Make Diagnosis
≥ 2	Objective clinical evidence of ≥ 2 lesions or objective clinical evidence of 1 lesion with reasonable historical evidence of a prior attack	None. Clinical evidence alone will suffice; additional evidence desirable but must be consistent with MS
≥ 2	Objective clinical evidence of 1 lesion	Dissemination in time, demonstrated by: 
 
• ≥1 T2 lesion in ≥ 2 MS typical CNS regions (periventricular, juxtacortical, infratentorial, spinal cord); OR
 
• Await further clinical attack implicating a different CNS site
 

1	Objective clinical evidence of ≥2 lesions	Dissemination in time, demonstrated by: 
 
• Simultaneous asymptomatic contrast-enhancing and non-enhancing lesions at any time; OR
 
• A new T2 and/or contrast-enhancing lesion(s) on follow-up MRI, irrespective of its timing; OR
 
• Await a second clinical attack
 

1	Objective clinical evidence of 1 lesion	Dissemination in space, demonstrated by 
 
• ≥1T2 lesion in at least 2 MS typical CNS regions (periventricular, juxtacortical, infratentorial, spinal cord); OR
 
• Await further clinical attack implicating a different CNS site AND
 
 Dissemination in time, demonstrated by 
 
• Simultaneous asymptomatic contrast-enhancing and non-enhancing lesions at any time; OR
 

		
 
• A new T2 and/or contrast-enhancing lesions(s) on follow-up MRI, irrespective of its timing; OR
 
• Aware a second clinical attack
 

0 (Progression from onset)		
One year of disease progression (retrospective or prospective) AND <math>\geq 2</math> out of 3 criteria:
 
 
• Dissemination in space in the brain based on <math>\geq 1</math> T2 lesion in periventricular, juxtacortical or infratentorial regions;
 
• Dissemination in space in the spinal cord based on <math>\geq 2</math> T2 lesions; OR
 
• Positive CSF
 

### What is an attack?

- Neurological disturbance of kind seen in MS
- Subjective report or objective observation
- $\geq 24$  Hours duration in the absence of fever or infection
- Excludes pseudo-attacks, single paroxysmal symptoms (multiple episodes of paroxysmal symptoms occurring over 24 hours or more are acceptable as evidence)
- Some historical events with symptoms and pattern typical for MS can provide reasonable evidence of previous demyelinating event(s), even in the absence of objective findings

**Determining Time Between Attacks:** 30 days between onset of event 1 and onset of event 2

### Provides Evidence for Dissemination in Space (DIS)?

- $\geq 1$  T2 lesion in at least 2 out of four areas of the CNS: periventricular, juxtacortical, infratentorial or spinal cord
- Gd enhancement of lesions is not required for DIS
- If a subject has a brainstem or spinal cord syndrome, the symptomatic lesions are excluded and do not contribute to lesion count

### What provides MRI Evidence of Dissemination in Time (DIT)?

- A new T2 and/or Gd-enhancing lesion(s) on follow-up MRI, with reference to a baseline scan, irrespective of the timing of the baseline MRI OR
- Simultaneous presence of asymptomatic Gd-enhancing and non-enhancing lesions at any time

**What is Positive CSF:** Oligoclonal IgG bands in CSF (and not serum) or elevated IgG index

2.4.6	Study Treatment Exposure and Compliance.....	21
2.4.7	Analyses of Pharmacokinetics.....	21
2.4.8	Analyses of Anti-Drug Antibody (ADA).....	22
2.4.9	Analyses of Immunoglobulins	22
2.5	Data Handling Conventions.....	22

2.5.1	Missing Data	22
2.5.2	Windows for Time Points	25
2.5.3	Unscheduled Visits	25
3	Interim Analysis.....	26

1 Overview and Investigational Plan

This statistical analysis plan (SAP) provides a detailed description of the statistical strategy for the “TG1101-RMS201” protocol Version 8.0 dated 10 October 2017. The goal of the SAP is to specify the statistical approaches to the analysis of study data.

1.1 Study Design and Randomization

This is a 52-week, phase IIa, placebo-controlled, multi-center study that is primarily designed to assess the optimal dosing, optimal infusion time as well as safety/tolerability of ublituximab (TG1101; UTX) in patients with RMS.

Subjects may be screened up to 4 weeks before first dosing date. Qualified subjects will receive ublituximab on Days 1, 15, and week 24. There will be at least four treatment cohorts in the study with 8 subjects (2 placebo and 6 ublituximab treatment; please see treatment schema) enrolled in each cohort.

A Data and Safety Monitoring Board (DSMB) will be established to safeguard the wellbeing of the subjects and to advise the Sponsor whether it is appropriate to expand the enrollment to a dosing cohort or to initiate next dosing cohort. Once a subject is qualified, the Site will contact the Sponsor or its designee for cohort assignment (treatment assignment). The Sponsor or its designee will issue the cohort assignment for the subject using the following procedures. If DSMB deems that a cohort is not appropriate (e.g., due to safety), enrollment to that cohort and all higher cohorts will be terminated and all future subjects will be enrolled to the lowest incomplete cohort. Upon completion of first two patients in each cohort (one on placebo and one on study drug) through 21 days, the DSMB will review safety data and assuming no safety concern is raised, the remaining qualified subjects will be enrolled into such cohort.

1.2 Objectives

1.2.1 Primary Objective

- To determine the level of B cell depletion by ublituximab in subjects with RMS
- To determine the optimal dose and infusion time for ublituximab in subjects with RMS

1.2.2 Secondary Objectives

- To examine the effect of ublituximab on the development of new Gadolinium- (Gd) enhancing lesions and new or enlarging T2 lesions at 24 and 48 weeks
- To evaluate the % of relapses in ublituximab-treated RMS subjects

[figure not shown]
- To determine immunogenicity
- To evaluate the safety of ublituximab, as determined by adverse events (AEs) and serious adverse events (SAEs), including MS worsening

1.3 Determination of Sample Size

1.4 Study Plan

Refer to the study protocol for TG1101-RMS201 for study schedule for analysis variables.

- Ublituximab (IV): Infusions on Days 1 and 15 and week 24
- Placebo (IV): Infusions on Days 1 and 15

2 Statistical and Analytical Procedures

2.1 Analysis Variables

Baseline for both efficacy and safety variables are defined as the last non-missing value on or before the first dose of Ublituximab.

2.1.1 Demographics and Baseline Characteristics

Demographic and other baseline characteristics

Demographic variables are gender (Male, Female), race (White, Black or African American, Asian, American Indian or Alaska Native, Native Hawaiian or Other Pacific Islander, Other, or Not Applicable due to country's legislation), age in years (quantitative and categorical variable: <38, and \geq 38 years) and Ethnicity (Hispanic or Latino, Not Hispanic or Latino, Not Reported, Unknown)

Medical and surgical history

Medical history data will be coded to “Preferred Term (PT)” and associated primary “System Organ Class (SOC)” using the Medical Dictionary for Regulatory Activities (MedDRA) version 23.0.

Disease characteristics at baseline

- Number of relapses experienced within past 1 year and 2 years (0, 1, 2, 3, and \geq 4), respectively
- Time since first diagnosis of MS (in years) to be derived as (Day of randomization – Day of first MS diagnosis) / 365.25
- Time since first symptoms of MS (in years) to be derived as (Day of randomization – day of first symptoms of MS) / 365.25
- Time since most recent relapse onset (in months) to be derived as (Day of randomization – day of most recent relapse onset) / (365.25 / 12)
- Baseline EDSS score
- Baseline EDSS (\leq 3.5, $>$ 3.5)
- Number of baseline Gadolinium (Gd)-enhancing lesions (0, \geq 1)
- Baseline T2 lesion count
- Baseline T2 lesion Volume
- Baseline brain volume

Multiple Sclerosis treatment history

- Received any MS therapy for at least 1 month (30 days) prior to enrollment (Yes, No)
- Prior Treatments for Current Diagnosis by Preferred Name
- Previous corticosteroid treatment for relapse
- Time since last corticosteroid treatment for relapse (months)

Vital signs and height

Vital signs are variables: weight in kg (quantitative variable and categorical variable: <50, \geq 50 - <100, \geq 100), height (m) and Body Mass Index (BMI) in weight[kg]/height[m²] (<30, \geq 30) calculated from weight and height.

Concomitant medications

All concomitant medications or concomitant medications (extension) are reported in the case report forms (CRF).

All medications will be coded using the World Health Organization-Drug Dictionary (WHO-DD).

- Concomitant medications are those taken at any time during the study treatment period, from the first study treatment use to the day of last study drug treatment, started before or during study treatment.
- Concomitant medications (extension) are those taken at any time between last study treatment and end of extension.

Technical details related to calculating dates, imputation for missing dates, etc. are described in Section [2.5](#).

[2.1.2 Study Treatment Exposure](#)

Treatment exposure for ublituximab/placebo is summarized with following variables:

- The total number of infusions of placebo
- The total number of infusions of ublituximab received over the 3 expected infusions.
- The overall number of infusions of ublituximab, number and percentage (based on all infusions) of infusions completed with/without interruption and infusions not completed.
- The number and percentage of patients (based on all patients with at least one infusion) with and without any infusion complication (interruption or stop).
- The percentage of planned total infusion received.

[2.1.3 Efficacy Variables](#)

[2.1.3.1 Primary Efficacy Variable](#)

The primary efficacy variable will be responder rate at week 4 (2 weeks after W3D15, the second scheduled infusion of ublituximab), where responders are subjects who have reduced B-cell depletion by $\geq 95\%$.

[2.1.3.2 Secondary Efficacy Variables](#)

The secondary efficacy variables are as follows:

- Number of new Gd-enhancing lesions at 24 and 48 weeks
- Number of new or enlarging T2 lesions at 24 and 48 weeks
- Annualized relapse rate (ARR)
- Relapse rate reduction (RRR)
- Percent of relapse free subjects

- Reduction in B cells (CD19+), memory (CD19+CD27+) and naïve (CD19+CD27-) B cells at baseline, day 1 (pre dose) and 2; week 2; Day15 (pre-dose); week 4 and every 4 weeks thereafter until the next infusion at week 24 (pre-dose and 2 days post-dose) 25, 28, 36, 40, 44 and 48
- To examine sustained B cell reduction during the first and third infusions
- Additional immune profiling (CD4+, CD8+, IL10 and NK cells) at baseline, day 1 (pre dose) and 2; week 2, Day 15 (pre-dose); week 4 and every 4 weeks thereafter until the next infusion at week 24 (pre-dose and 2 days post dose) 25, 28, 36, 40, 44 and 48
- PK (ADME) profile of ublituximab at day 1 (pre-dose); week 2; day 15 (pre-dose); weeks 4, 24 (pre-dose) and 25

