Safety Endpoints	All AEs will be reported and evaluated during the treatment period using National Cancer Institute (NCI) version 4.0 grading system; the number and severity of infusion-associated events, defined as AEs reported during or within 24 hours of an infusion; the number and severity of infectious AEs; any clinically significant changes in laboratory or vital sign measurements; the incidence of anti-drug antibodies (antibodies developed against ublituximab) to assess safety over the 52-week trial.
Study Design	This is a 52-week, phase IIa, placebo-controlled, multi-center study that is primarily designed to assess the optimal dosing, optimal infusion time as well as safety/tolerability of ublituximab (TG1101; UTX) in patients with RMS.

Subjects may be screened up to 4 weeks before first dosing date. Qualified subjects will receive ublituximab on Days 1, 15, and week 24. There will be at least four treatment cohorts in the study with 8 subjects (2 placebo and 6 ublituximab treatment; please see treatment schema) enrolled in each cohort. Subjects within each cohort will receive either placebo or study drug dosing on Days 1 and 15 and week 24 per dosing schema (please see table below). Additional dose ranging cohorts may be explored and expansion cohorts at selected doses are contemplated.

A Data and Safety Monitoring Board (DSMB) will be established to safe guard the wellbeing of the subjects and to advise the Sponsor whether it is appropriate to expand the enrollment to a dosing cohort or to initiate next dosing cohort. The DSMB may recommend to the Sponsor to terminate the enrollment to a treatment cohort for safety concerns or otherwise. For example, the DSMB may recommend early termination of enrollment to a dosing cohort that is higher than the optimal treatment cohort after the optimal dosing is determined or a cohort that is considered without meaningful clinical benefit.

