**Table 7: Treatment Schema for Placebo Subjects after Day 28**

Cohort	Subjects	Day 1/ infusion time	Day 15/ infusion time	Week 24/ infusion time
1a	Pbo patients from Cohort 1	150 mg UTX / 4h	450 mg UTX / 3h	450 mg UTX / 1.5h
2a	Pbo patients from Cohort 2	150 mg UTX / 4h	450 mg UTX / 1.5h	450 mg UTX / 1h
3a	Pbo patients from Cohort 3	150 mg UTX / 4h	450 mg UTX / 1h	600 mg UTX / 1h
4a	Pbo patients from Cohort 4	150 mg UTX / 3h	600 mg UTX / 1h	600 mg UTX / 1h
5a	Pbo patients from Cohort 5	150 mg UTX / 2h	600 mg UTX / 1h	600 mg UTX / 1h
6a	Pbo patients from Cohort 6	150 mg UTX / 1h	600 mg UTX / 1h	600 mg UTX / 1h

---

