#### 5.2.1.1 INFUSION RELATED REACTIONS AND INFUSION RATE GUIDANCE

---

Infusion related reactions, including severe reactions, have been reported with ublituximab administration in subjects with CLL and NHL. Guidelines are provided below for subjects who experience such reactions. Symptomatic infusion reactions, despite premedication, may be treated at the discretion of the Principal Investigators using the following or other appropriate treatments: oral acetaminophen 650 mg, corticosteroids, antihistamines, oxygen, and bronchodilators.

The following are recommended infusion rate reduction/delay guidelines for subjects who experience severe Infusion Related Reactions (IRR's) that require treatment interruption. The final decision for the infusion rate reduction/delay or discontinuation resides with the treating investigator. Infusion rates should be considered targets for each respective cohort. If the treating investigator decides to interrupt the infusion or slow the infusion rate, then the reduction/delay and the reason for it must be noted on the eCRF and infusion log.

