## 2nd infusion

### 2ND INFUSION OF UBLITUXIMAB OR PLACEBO

Cohort	Ublituximab Dose	Total volume to be infused	Infusion rate		
			T0 to T1H	T1H to T2H	T2H to T3H
1	450	250 mL	25 mL/H	75 mL/H	150 mL/H

Cohort	Ublituximab Dose	Total volume to be infused	Infusion rate	
			T0 to T30 min	T30 min to T90min
2	450	250 mL	100 mL/H	200 mL/H

Cohort	Ublituximab Dose	Total volume to be infused	Infusion rate	
			T0 to T30min	T30min to T60min
3	450 mg	250 mL	100 mL/H	400 mL/H

Cohort	Ublituximab Dose	Total volume to be infused	Infusion rate	
			T0 to T30min	T30min to T60min
4-6	600 mg	250 mL	100 mL/H	400 mL/H

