## 3rd infusion

### 3RD INFUSION OF UBLITUXIMAB

Cohort	Ublituximab Dose	Total volume to be infused	Infusion rate	
			T0 to T30min	T30min to T90min
1	450	250 mL	100 mL/H	200 mL/H

Cohort	Ublituximab Dose	Total volume to be infused	Infusion rate	
			T0 to T30min	T30min to T60min
2	450	250 mL	100 mL/H	400 mL/H

Cohorts	Ublituximab Dose	Total volume to be infused	Infusion rate	
			T0 to T30min	T30min to T60min
3-6	600mg	250 mL	100 mL/H	400 mL/H

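### Infusion time is a primary objective, but no SAP summary table ties reactions or interruptions to the infusion that was sped up

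*SAP*

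**What the plan says.** Both documents list as a primary objective "To determine the optimal dose and infusion time for ublituximab in subjects with RMS". Protocol Table 6 sets dose and time for Day 1, Day 15 and Week 24 in six cohorts. Table 7 gives the placebo subjects the same schedule after Day 28, down to the row for "Pbo patients from Cohort 6".

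The protocol plans two kinds of summary at the level of the infusion. The synopsis makes a safety endpoint of "the number and severity of infusion-associated events, defined as AEs reported during or within 24 hours of an infusion". Section 9.7 plans dose modification by infusion as well as overall, and the proportion of subjects completing each infusion.

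The SAP is coarser. Section 2.1.2 lists the "number and percentage (based on all infusions) of infusions completed with/without interruption and infusions not completed" and the number of patients with or without any infusion complication. Section 2.4.5.1 presents adverse events, including those leading to interruption and those of special interest, by cohort and total. It names no table for events within 24 hours of an infusion and none by infusion number. Actual infusion duration is not listed as a variable.

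Protocol 5.2.1.1 adds that "Infusion rates should be considered targets for each respective cohort". If an infusion is slowed or interrupted, "the reduction/delay and the reason for it must be noted on the eCRF and infusion log".

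**The concern.** A cohort's infusion time is three times, one per infusion, and each cohort step alters only one or two of the infusions. A row that adds all three mixes the infusion under test with infusions given exactly as in the neighbouring cohort, or with a second infusion that changed at the same step. The reader of the final tables would see whether a cohort had more trouble, but not at which infusion. That second fact is what a choice of infusion time needs.

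Two other outputs do not fill the gap. The dose-limiting toxicity table leaves out first-infusion reactions of Grade 3 or higher that do not affect continuation (protocol 5.1.1), and the first infusion is the one accelerated in Cohorts 4 to 6. Its 4-week window also excludes Week 24. The special-interest event tables are arranged by category and preferred term, using terms that the sponsor selects and reports in the study report.

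**Working it through.** The documents state no figure for this point, so there is none to reproduce. The check compares the schedules and then measures what pooling does.

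**1. What changes at each step (protocol Table 6)**

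- Cohort 1 to 2: Day 15 time 3 h to 1.5 h, and Week 24 time 1.5 h to 1 h.
- Cohort 2 to 3: Day 15 time 1.5 h to 1 h, and Week 24 dose 450 to 600 mg.
- Cohort 3 to 4: Day 1 time 4 h to 3 h, and Day 15 dose 450 to 600 mg.
- Cohort 4 to 5: Day 1 time 3 h to 2 h only.
- Cohort 5 to 6: Day 1 time 2 h to 1 h only.

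**2. Peak delivery rate** = mL/h x dose / 250 mL, from the cohort-specific flow-rate tables in protocol 8.1.3.1, including those headed "2ND INFUSION OF UBLITUXIMAB OR PLACEBO" and "3RD INFUSION OF UBLITUXIMAB".

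- First infusion: 100, 150, 225 and 450 mL/h x 150/250 = 60 (Cohorts 1 to 3), 90, 135 and 270 mg/h.
- Day 15: 150, 200 and 400 mL/h x 450/250 = 270, 360 and 720 mg/h (Cohorts 1 to 3); 400 x 600/250 = 960 mg/h (Cohorts 4 to 6).
- Week 24: 200 and 400 mL/h x 450/250 = 360 and 720 mg/h (Cohorts 1 and 2); 400 x 600/250 = 960 mg/h (Cohorts 3 to 6).

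From Cohort 4 to 6 the first infusion rises 270/90 = 3 times and the other two stay fixed. In each of the first three steps, two infusions rise together.

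**3. Infusion-level row.** If all three infusions are given, the pooled rate is (p1 + p2 + p3)/3, so a change at one infusion appears at one third. Assume first-infusion interruption of 10% and 40% in two cohorts, with 5% at each other infusion:

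- (10 + 5 + 5)/3 = 6.7%
- (40 + 5 + 5)/3 = 16.7%

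The 30-point difference becomes 10 points. The loss is the same for any common rate at the other two infusions.

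**4. Patient-level row.** Assuming independence, P(any) = 1 - (1 - p1)(1 - b)^2, where b is the rate at each other infusion.

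- b = 5%: 18.8% against 45.9%, a difference of 27 points.
- b = 10%: 27.1% against 51.4%, a difference of 24 points.

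This row dilutes much less, but it does not name the infusion.

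**5. What the rows cannot separate.** Take Cohort 2 with 8 subjects (6 plus 2 crossover) and 8 x 3 = 24 infusions. Suppose four different subjects are each interrupted once. If all four are at Day 15, or all four at Week 24, the rows are the same: 4/24 = 17% by infusion and 4/8 = 50% by patient. By infusion, one case is 4/8 and 0/8, the other 0/8 and 4/8. Both infusions were shortened at that step.

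**6. Precision of the split counts** (exact 95% intervals): 4/8, 16% to 84%; 0/8, 0% to 37%; 3/6, 12% to 88%; 0/6, 0% to 46%.

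**The case against.** The other side has four good arguments.

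- The information exists. The SAP's event listings show date and day of onset, and with 6 to 8 subjects per cohort each event can be matched to an infusion by hand. Cohorts 4, 5 and 6 differ only in first-infusion time, so a difference between those columns points there by design, apart from chance. This stands. A reader might infer that the effect of infusion speed cannot be seen at all; the documents do not support that.
- Protocol 9.7 already plans completion and dose modification by infusion, nothing in the SAP withdraws it, and a percentage base of all infusions does not forbid a finer layout. The table shells that protocol section 9 assigns to the SAP do not appear in the text available, so the final layout cannot be confirmed. This makes part of the point a carry-over omission. It does not supply the missing table, and 9.7 does not cover the 24-hour event endpoint.
- Protocol 10.1 presents safety variables by dose actually received, and every first infusion is 150 mg while later ones are 450 or 600 mg. That wording is ambiguous. SAP 2.4.5 organises safety by cohort, and a split by dose would not separate Day 15 from Week 24 where both doses are equal.
- The study is unpowered and descriptive, and escalation rests on total safety data (protocol 5.1.3). This stands and limits the consequence. Small numbers are still no reason to pool counts that can be shown plainly.

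**Conclusion.** The point holds for the SAP's summary tables. None links reactions or interruptions to the infusion that was accelerated, and two protocol plans that would have done so are not carried over. The loss is greatest in the steps from Cohort 1 to 4, where two infusions change together and cohort rows cannot separate them. From Cohort 4 to 6 it is smaller, because the design itself points to the first infusion.

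The one-third dilution applies to the infusion-level row only. A reader might extend it to everything the SAP reports, but in the assumed example the patient-level row keeps 24 to 27 of 30 points. A reader might also infer that a slowed infusion is counted as completed without interruption. That is likely, but the SAP does not define interruption.

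The assumptions are that all three infusions are given, that crossover subjects are counted with their cohort (18 infusions instead of 24 if they are not), that exposure rows are shown by cohort, and the illustrative interruption rates. The documents give no interruption rates. DSMB escalation is unaffected. The change is worth making because it serves a primary objective at little cost, not because any test or decision rule would change.

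**What to change.** In SAP 2.1.2 and 2.4.5.1, add one descriptive table block by cohort and by first, second and third ublituximab infusion. The denominator is subjects who started that infusion. Show:

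- (a) subjects with infusion-associated adverse events, all grades and Grade 3 or higher, using the protocol's 24-hour window, or onset on the infusion day or the next day if onset time is not collected;
- (b) infusions slowed, interrupted, not completed and completed;
- (c) actual infusion duration where recorded.

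Count a first infusion finished on Day 2 as one infusion, with the window running from its end. Keep the pooled rows as totals. The exemption in protocol 5.1.1 need not change.

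The cost is one table block and a flag linking each event to an infusion. Slowing or interruption and its reason must already be recorded on the eCRF. The listings mention day of onset but not time, so the day-based rule may be needed; it would attribute some events beyond 24 hours to the infusion. Counts in 6 to 8 subjects would support description only.
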